4 STUDY DESIGN

4.1 Description

This is a Phase II non-randomized pilot study meant to establish preliminary reference response rate and duration of response for subjects with recurrent prostate cancer treated with salvage oligometastasectomy and/or radiotherapy. Treatment decisions will be based on molecular imaging (e.g., fluciclovine PET/CT or PSMA PET/CT scan or other per PI discretion): subjects with nodal disease only will be treated with oligometastasectomy, subjects with bone disease only will be treated with SBRT, and subjects with a combination of nodal and bone disease will receive both treatment. Response rates and durations will be based on PSA and imaging.

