4.2 Number of Subjects

A total of twenty (20) subjects will be enrolled on this study.

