11 STATISTICAL CONSIDERATIONS

11.1 Sample size determination

The planned sample size is N = 20 evaluable subjects. The primary outcome variable of reduction in PSA $\geq 50\%$ at 6 months will be analyzed descriptively via 90% and 95% exact binomial confidence intervals. No hypothesis test will be performed on the primary outcome

variables. The sample size is justified by the width of the 95% confidence intervals. We anticipate that the PSA 50% response rate at 6 months will be 30% based on the results published by Siriwardana, as their PSA response at 6 weeks and 12 months was 43% and 23% respectively. However, the definition used here is somewhat different than the definition in that clinical study. If the observed PSA 50% response rate is 30% (6/20), the 95% exact binomial confidence interval (Clopper-Pearson) will be 12% to 54 %. With 20 evaluable subjects the maximum width of a 95% exact binomial confidence interval is 46% (27% to 73%) and occurs when the observed response rate is 50% (10/20).

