11.3 Statistical Hypotheses and Analyses

This study is establishing baseline data for patients who have no defined standard of care therapy. All study data will use descriptive statistics and will be exploratory only.

Since this study is not using any hormonal therapy, we expect that using PSA analysis will be accurate and provide an early readout regarding the potential efficacy and clinical utility of this approach.

Primary Objective

The primary endpoint is the proportion of subjects with a reduction in PSA $\geq 50\%$ 6 months after completion of all treatment (salvage and adjuvant therapy). The observed proportion and a 95% exact binomial confidence interval will be reported for the entire group of evaluable patients (Arms A, B and C together) as well as for each cohort separately.

Secondary Objectives

1. 95% exact confidence intervals will be reported for the observed proportions with reductions in PSA $\geq 50\%$ 12 months after and $\geq 90\%$ 6 and 12 months after completion of all treatment (salvage and adjuvant therapy). This will be done for the entire group of evaluable patients (Arms A, B and C together) as well as for each Arm separately.
2. The proportion of subjects without PSA progression (defined using Prostate Cancer Working Group 3 Criteria PCWG3), will be evaluated every 3 months for 3 years after completion of all treatment (salvage and adjuvant therapy) and analyzed using Kaplan-

Meier methodology. This will be done for the entire group of evaluable patients (Arms A, B and C together) as well as for each Arm separately.

3. The time from study enrollment until the date of confirmed radiographic disease progression as defined by RECIST 1.1 and PCWG3 will be analyzed using Kaplan-Meier methods. This will be done for the entire group of evaluable patients (Arms A, B and C together) as well as for each Arm separately.
4. The time from study enrollment to the initiation of ADT will be analyzed using Kaplan-Meier methods. This will be done for the entire group of evaluable patients (Arms A, B and C together) as well as for each Arm separately.
5. The proportion of patients with a PSA ≤ 0.2 ng/mL will be evaluated 6 and 12 months after completion of all treatment (salvage and adjuvant therapy) in the subset of patients who have previously undergone prostatectomy. This will be done for the entire group of evaluable patients (Arms A, B and C together) as well as for each Arm separately.

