6. The number and proportions of subjects with AEs and SAEs as defined by CTCAE version 5.0 will be tabulated both for the entire safety population and also stratified by Arm.
7. 95% confidence intervals will be reported for summary scales of the quality of life (QOL) questionnaires (FACT-P and Expanded Prostate Cancer Index Composite EPIC-26) measured at screening, response assessment visit, and each follow up visit. This will be done for the entire group of evaluable patients (Arms A, B and C combined) and also stratified by Arm. Normal approximations will be used for computation of confidence intervals.

Exploratory Objective

Genomic alterations or abnormal protein expression that correlate with radiation resistance or predilection for early metastasis and worse overall prognosis will be tabulated.

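### Normal-approximation 95% intervals for the quality-of-life scales will be too narrow in the small Arms; specify the t quantile and show n

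*Combined protocol and SAP*

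**What the plan says.** Section 11.3, Secondary Objectives item 7, states that "95% confidence intervals will be reported for summary scales of the quality of life (QOL) questionnaires", covering FACT-P and EPIC-26 at screening, the response assessment visit and each follow-up visit. On the analysis sets it says "This will be done for the entire group of evaluable patients (Arms A, B and C combined) and also stratified by Arm". On the method it says only "Normal approximations will be used for computation of confidence intervals". It names no quantile and no small-sample correction.

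On size, Section 4.2 says "A total of twenty (20) subjects will be enrolled on this study" and Section 11.1 says "The planned sample size is N = 20 evaluable subjects". Arms follow the site of disease. Section 4.1 says "subjects with nodal disease only will be treated with oligometastasectomy, subjects with bone disease only will be treated with SBRT", and subjects with both kinds of disease receive both treatments. No Arm size or quota is given.

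On the standing of the results, Section 11.3 says "All study data will use descriptive statistics and will be exploratory only".

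**The concern.** A normal multiplier of 1.96 is right when the SD is known or the sample is large. Here the SD must be estimated from 20 subjects at most, and from far fewer within an Arm. The estimated SD adds uncertainty that 1.96 ignores, so the interval is too short and covers less than its label says.

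Quality of life is a stated secondary objective (Section 1.2.7), and the trial is meant to supply reference data for later studies (Section 2). A per-Arm interval that is too narrow would make those data look more precise than they are.

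The numbers can also fall with time. Questionnaires run every 3 months for 3 years (Section 9.3). Subjects taken off treatment for treatment failure are then followed for toxicity only (Section 6.4.1), and starting new anti-cancer therapy takes a subject off study (Section 6.4.2).

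**Working it through.** **The plan's own precision figures.** The documents give no precision or coverage figure for the quality-of-life intervals. The figures they do give are the Clopper-Pearson limits in Section 11.1. The lower limit is the 0.025 quantile of Beta(x, n − x + 1), and the upper limit is the 0.975 quantile of Beta(x + 1, n − x).

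- 6/20: 11.9% to 54.3% (plan: 12% to 54%).
- 10/20: 27.2% to 72.8%, width 45.6%, the largest over all outcomes (plan: 27% to 73%, width 46%).

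Both reproduce.

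**Inputs for the quality-of-life check.** Nominal level 95% and normal approximation (Section 11.3, item 7); 20 subjects in total (Sections 4.2 and 11.1); three Arms of unstated size (Section 4.1). Assumptions: the interval is mean ± 1.96 × s/√n with s estimated from the same n scores, and scores are normal.

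**Formula.** (mean − true mean)/(s/√n) has a t distribution with n − 1 degrees of freedom, so

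coverage(n) = P(|T with n − 1 df| < 1.96) = 2F(1.96; n − 1) − 1.

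The t interval is wider by the factor t(0.975; n − 1)/1.96. A check by hand at n = 3, where the 2-df distribution has a closed form: coverage = 1.96/√(2 + 1.96²) = 1.96/√5.8416 = 0.811.

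| n | Coverage of mean ± 1.96 SE | t multiplier | Width of t interval relative to 1.96 |
|---|---|---|---|
| 2 | 70.0% | 12.706 | 6.48 |
| 3 | 81.1% | 4.303 | 2.20 |
| 4 | 85.5% | 3.182 | 1.62 |
| 5 | 87.8% | 2.776 | 1.42 |
| 6 | 89.3% | 2.571 | 1.31 |
| 7 | 90.2% | 2.447 | 1.25 |
| 10 | 91.8% | 2.262 | 1.15 |
| 14 | 92.8% | 2.160 | 1.10 |
| 20 | 93.5% | 2.093 | 1.07 |

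**What holds without knowing the Arm sizes.**

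- If every Arm had 7 or more, the total would be at least 3 × 7 = 21, which exceeds 20. So at least one Arm has 6 or fewer, with coverage of 89.3% or less.
- If two Arms had 11 or more, the total would be at least 2 × 11 = 22, which exceeds 20. So at least two Arms have 10 or fewer, with coverage of 91.8% or less.

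Coverage falls as n falls, so these are upper bounds for any Arm large enough to have an interval (n of 2 or more).

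**Range over illustrative splits (assumed).** A 7/7/6 split gives 90.2%, 90.2% and 89.3%. A 10/7/3 split gives 91.8%, 90.2% and 81.1%. A 14/3/3 split gives 92.8%, 81.1% and 81.1%.

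**Sensitivity to skew (assumed).** The scales are bounded and scores may be skewed. A simulation of 400,000 samples per size from a Beta(8, 2) score, a shape not taken from the documents, gave:

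| n | 1.96 interval | t interval |
|---|---|---|
| 3 | 78.7% | 93.1% |
| 5 | 85.9% | 93.1% |
| 10 | 90.6% | 93.7% |
| 20 | 92.8% | 94.3% |

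The t interval is better at every size but stays a little below 95%.

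**The case against.** Several points can fairly be made in the plan's defence.

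*No quantile is named.* Item 7 does not say 1.96, and a t interval also rests on normality. This stands as a limit on certainty. A t interval is usually described as assuming normal data, though, not as a normal approximation, so 1.96 is the natural reading. If t was intended, the text is ambiguous and the same sentence settles it.

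*Arm sizes are unknown.* A reader might infer that the per-Arm intervals will cover 81% to 92%. The documents do not support that as a fact: it corresponds to Arms of 3 to 10 subjects. An Arm of 2 would cover 70%, and an Arm of 14 would cover 92.8%. What follows from the documents is the pair of upper bounds shown in the working.

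*The pooled interval is nearly right.* This stands. At n = 20 the shortfall is 95% − 93.5% = 1.5 percentage points.

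*The quality-of-life intervals are not shown to be the exception.* A reader might infer that they alone use a large-sample method. Section 11.3 specifies exact intervals for the primary endpoint and for item 1. Item 5 (PSA ≤ 0.2 ng/mL) and the Kaplan-Meier items 2 to 4 state no interval method, so the contrast cannot be drawn.

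*Nothing depends on these intervals.* No test, threshold or stopping rule uses them, and the sample size rests on the PSA proportion. This stands and limits the weight of the point. It does not remove it, because in a descriptive study the estimates and intervals are the result.

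**Conclusion.** The point holds for the per-Arm intervals. On the plain reading of item 7, and with normal scores, no allocation of 20 subjects to three Arms avoids it: at least two Arms are at 91.8% or less, and at least one is at 89.3% or less. An Arm of 3 to 5 subjects would be at 81% to 88%. Loss of subjects or questionnaires at later visits would lower these figures further. The pooled interval has only a minor shortfall (93.5% at n = 20).

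The conclusion rests on two assumptions: that the multiplier is 1.96, and that scores are roughly normal. The bounds need no assumption about Arm sizes; the 81% to 88% range does. It would be too much to say that a t interval makes coverage exactly 95%. That is true for normal scores, but for skewed scores it improves coverage without fully restoring it.

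This should be corrected because the stated method gives error bars that are too narrow and the change is easy. It does not affect the primary endpoint or any decision in the trial.

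**What to change.** Replace the last sentence of item 7 in Section 11.3 with:

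> Intervals for mean scale scores will use the t distribution with n-1 degrees of freedom at each visit, pooled and by Arm, limited to the range of the scale; n will be shown with every interval.

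Limiting the interval to the scale removes impossible values but does not improve coverage. Showing n lets readers see when an Arm is too small for its interval to be informative.

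The change needs no new data and alters no patient procedure. Its cost is wider intervals: about 7% at n = 20, 15% at n = 10, 42% at n = 5 and 120% at n = 3. In the smallest Arms that is a large increase, and it reflects how little so few scores can show.

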1.3 Exploratory Objective(s)

To assess the correlation of molecular biomarkers with clinical response and resistance to surgery and radiation therapy.

Exploratory Endpoint(s): Evaluation for genomic alterations or abnormal protein expression that correlates with radiation resistance or predilection for early metastasis and worse overall prognosis.

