14 CORRELATIVE STUDIES

Optional Tissue and blood may be collected at the time points notated in the Study Calendar. Samples will be used to identify biomarkers of response or resistance to the prescribed treatments. For those patients with both archival and fresh tissue, comparison between the pre- and post-treatment tissue will be performed as applicable. All correlative tissue collection is optional and not mandatory.

Testing may include, but is not limited to:

- Genomic alterations such as deletions, mutations or amplifications;
- Transcriptome RNA assessments;
- Immunohistochemistry testing for protein expression.
- Cytokine/chemokines
- Circulating free DNA (cfDNA)
- Circulating tumor cells (CTC) detection, enumeration, and characterization

Specimen collection and processing instructions can be found in the lab manual.

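### Section 11.3 tabulates markers that correlate with outcome and does not require the number examined or the null results, so chance findings in the table cannot be gauged

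*Combined protocol and SAP*

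**What the plan says.** The exploratory analysis plan is one sentence at the end of Section 11.3: "Genomic alterations or abnormal protein expression that correlate with radiation resistance or predilection for early metastasis and worse overall prognosis will be tabulated".

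Three other places bear on how to read it.

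- Section 1.3 states the objective: "To assess the correlation of molecular biomarkers with clinical response and resistance to surgery and radiation therapy".
- Section 14 gives the purpose of the specimens: "Samples will be used to identify biomarkers of response or resistance to the prescribed treatments". Its list of assays opens with "Testing may include, but is not limited to" and has six items. Two match the Section 11.3 sentence: "Genomic alterations such as deletions, mutations or amplifications" and "Immunohistochemistry testing for protein expression". The other four are RNA, cytokines or chemokines, cell-free DNA and circulating tumour cells.
- On numbers, Section 11.1 says "The planned sample size is N = 20 evaluable subjects", and Section 14 says "All correlative tissue collection is optional and not mandatory".

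Section 11.3 also states at its start that all analyses are descriptive and exploratory. The documents give no marker count, no candidate list and no measure or threshold for correlation. For this purpose they do not define radiation resistance, early metastasis or worse prognosis. They do not say what happens to markers that show no association.

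**The concern.** A table whose rows are chosen because they showed an association differs from a table of everything examined. Under the first rule, some rows may be there by chance, and their effects look large because a large effect is what admitted them. Without the number examined, a reader cannot compare the rows found with the number expected from chance alone.

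The other endpoints in Section 11.3 are reported whatever they show; only this one is worded as conditional on the result. The Background (Section 2) says the trial should serve as a basis for later investigations. A marker carried forward from a result-selected table would start with an inflated effect and no record of how many candidates it was picked from.

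**Working it through.** **1. The plan's own figures.** The documents give no figure for the marker analysis. The Section 11.1 precision figures reproduce with Clopper-Pearson limits: 6/20 gives 11.9% to 54.3% (stated 12% to 54%), and 10/20 gives 27.2% to 72.8%, width 45.6% (stated 27% to 73%, 46%). The defect is in the tabulation rule, not in these numbers.

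**2. Which data decide the correlation.** The Section 11.3 sentence alone could mean markers already known from elsewhere to carry a poor prognosis. Sections 1.3 and 14 point the other way: correlation is to be assessed, and markers identified, from this trial's samples, and no prior list is given. On that reading, the observed association decides entry to the table.

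**3. Inputs for size.** From the documents: 20 evaluable subjects, and an anticipated response of 30%, used here as an illustrative split of 6 responders and 14 non-responders. Assumed, because the documents give neither: the number of markers m, and a two-sided 5% screen as the meaning of correlation. All markers are taken as independent and truly unrelated to outcome.

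**4. Full 5% screen.** Expected chance entries = 0.05 × m. Probability of at least one = 1 − 0.95^m.

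| m | Expected | At least one |
|---|---|---|
| 6 | 0.3 | 26% |
| 20 | 1.0 | 64% |
| 50 | 2.5 | 92% |
| 100 | 5.0 | 99% |

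**5. Binary markers.** For alterations scored present or absent, Fisher's exact test at 6 v 14 does not reach 5%. Summing the binomial probabilities of all tables with p ≤ 0.05 gives the attained error α; expected entries are α × m, and the probability of at least one is 1 − (1 − α)^m.

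| Marker prevalence | α | m = 50: expected, at least one | m = 100: expected, at least one |
|---|---|---|---|
| 10% | 0.4% | 0.2, 20% | 0.4, 36% |
| 30% | 2.2% | 1.1, 67% | 2.2, 89% |
| 50% | 3.2% | 1.6, 81% | 3.2, 96% |

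Step 4 is therefore an upper case for such markers.

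**6. A purely descriptive screen.** If a marker entered the table because its frequency differed by at least 30 percentage points between responders and non-responders, with no test, the chance of entry for a null marker at 6 v 14 is 4%, 17% and 25% at prevalence 10%, 30% and 50%.

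**7. Exaggeration.** For a continuous marker in 20 subjects, nominal p < 0.05 needs |r| of about 0.44, so every null marker that passes shows at least that. In simulation the median largest |r| among null markers is about 0.47 for 20 markers, 0.59 for 100 and 0.67 for 500. With only 10 subjects sampled, these become about 0.66, 0.79 and 0.86.

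**The case against.** The strongest reply is that the sentence is ambiguous rather than a stated screening rule. It does not contain the word only, and it does not forbid reporting the other markers or the number examined. It could describe a class of adverse-prognosis markers whose frequency is to be tabulated. In support, overall prognosis matches no endpoint in Sections 1.2 or 10, so the trial has no stated outcome on which to screen for it. The analysis is also declared descriptive and exploratory, uses optional samples, and informs no decision within the trial.

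Much of this stands. A reader might infer that the table will fill with chance findings, or that the plan hides how many markers were tested. The documents support neither. With no marker count or criterion, the expected number of chance entries runs from well under one to several, and silence about the number examined is not concealment. A reader might also apply the sentence to all six assay types in Section 14. It names only genomic alterations and protein expression; the remaining assays have no clearly stated analysis, which is a separate gap.

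What does not stand is that the exploratory label settles the matter. It excuses the absence of formal error control. It does not tell the reader of a descriptive table what was examined, and Sections 1.3 and 14 make selection on the trial's own data the more natural reading.

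**Conclusion.** The point holds as a minor one. Followed as written and read with Sections 1.3 and 14, Section 11.3 gives a table selected on the observed association, from an open list, in at most about 20 subjects and possibly fewer, with no required denominator. The table may contain chance findings with exaggerated effects whose number cannot be judged.

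The size is conditional. It ranges from 0.3 expected chance entries for 6 markers to 5 for 100 under a full 5% screen, and from 0.4 to 3.2 for 100 binary markers under Fisher's exact test. These figures rest on assumed marker counts, independence, no true associations, a 5% criterion and, for the binary case, a 6 v 14 split. No primary or secondary result is affected.

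**What to change.** Before marker results are known, replace the exploratory sentence in Section 11.3 with:

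*All genomic alterations and protein-expression markers examined will be tabulated against the trial's stated outcomes (PSA response, PSA progression and radiographic progression), regardless of the observed association, with the number of subjects assayed, an estimate and interval suited to the marker type, and the total number of markers examined. High-dimensional assays will be summarised with the number of features examined and full results in a supplement. Any analysis of radiation resistance will be limited to subjects who received radiotherapy.*

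The last sentence is needed because PSA response cannot stand in for radiation resistance in everyone: under Section 6.2.3.1, a subject with a complete PSA response after resection requires no further treatment, so that response may say nothing about radiation.

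The cost is a longer supplementary table. No new samples and no multiplicity correction are needed.

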12 REGISTRATION GUIDELINES

Study related screening procedures can only begin once the subject has signed a consent form.

Subjects must meet all of the eligibility requirements listed in Section 5 prior to registration.

Subjects must be registered before receiving any study treatment and must begin treatment as soon as possible after registration.

To register eligible subjects on study, complete a Clinical Trials Office Subject Registration Form and submit to [contact].

13 DATA SUBMISSION SCHEDULE

The Case Report Forms (CRFs) are a set of (electronic or paper) forms for each subject that provides a record of the data generated according to the protocol. CRF's should be created prior to the study being initiated and updated (if applicable) when amendments to the protocol are IRB approved.

These forms will be completed on an on-going basis during the study. The medical records will be

Short Title: Image Guided Salvage Oligometastasectomy and Radiation Therapy in Recurrent Prostate Cancer (SOAR)

Version Date: 10NOV2021

source of verification of the data. During the study, the CRFs will be monitored for completeness, accuracy, legibility and attention to detail by a member of the Research Compliance Office. The CRFs will be completed by the Investigator or a member of the study team as listed on the Delegation of Duties Log. The data will be reviewed no less than annually by the Data and Safety Monitoring Committee. The Investigator will allow the Data and Safety Monitoring Committee or Research Compliance Office personnel access to the subject source documents, clinical supplies dispensing and storage area, and study documentation for the above-mentioned purpose. The Investigator further agrees to assist the site visitors in their activities.

Data capture should be restricted to endpoints and relevant subject information required for planned manuscripts.

